1.1. Rationale and Objective: While there is support in the literature for beneficial effect of XO inhibitor therapy on GFR and BP in pediatric CKD, the degree of expected change in GFR based on disease etiology is uncertain. Therefore, we propose a randomized controlled trial of hyperuricemic pediatric CKD participants in a 2:1 allocation between Allopurinol and standard of care (SOC) therapy, and stratified by disease etiology (cohort A: non-glomerular, cohort B: glomerular). Randomization procedure will be blinded, but the allocation will be unblinded to investigator and participant because of the lack of placebo. Allopurinol will be titrated to reach a normal range of serum UA 3-5 mg/dL by 6 months. Local SOC practice for pediatric CKD includes control of blood pressure with anti-hypertensives, control of acidosis, control of proteinuria, and frequent laboratory monitoring to measure the rate of renal function decline. The primary outcome of Aim 1A is change in GFR between baseline and 6 months by treatment group. The secondary outcomes are change in serum UA, and change in BP over the same time. An exploratory sub-aim (Aim 1B) will identify and compare GFR change by cohort characteristics (disease etiology, proteinuria, and race) that may influence future trial designs.

1.2. Experimental Design (Table 1): We will conduct a 6-month randomized treatment (Allopurinol) vs. SOC clinical trial to measure change in GFR over time in pediatric hyperuricemic CKD participants. We will conduct this study after obtaining appropriate consent and assent. Our recruitment pool will include all patients receiving medical care from the CHoR Pediatric Nephrology Division, new and recurring outpatient encounters. The division currently sees approximately 3,500 outpatient encounters per year. The study visits will coincide with SOC visits with the possible exception of visit V1A (some but not all participants will normally be seen for SOC 1 month after the baseline visit). The following inclusion and exclusion criteria apply:

- Inclusion Criteria: CKD stage 1-5; Age 2-20 years old at time of enrollment; Hyperuricemic
- Exclusion Criteria: Contraindication to Allopurinol; Elevated baseline liver function tests; Receiving acute or chronic dialysis; Primary metabolic disorder; Sickle cell disease; Autosomal Dominant Polycystic Kidney Disease; Cystinosis; Bartter or Gitelman Disease; Pregnant or nursing.

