At baseline, demographic and anthropometric data, CKD disease etiology and duration since diagnosis, current medications, and presence of proteinuria or hypertension will be collected. At baseline and 6 months, casual clinic BP will be obtained (the average of three measurements) for hypertension assessment. Serum and non-invasively obtained urine will be collected at baseline, 3, and 6 months for basic or comprehensive metabolic panel, UA, cystatin C and creatinine-based GFR measurements. An additional serum and urine sample for purposes of dose titration and safety will be collected from the treatment group but not control at Visit V1A. The residual serum and urine samples will be bio-banked for the analyses of Aim 2. Adverse events will be collected and adherence will be measured at the V1A, V2, and V3 visits by pill count and through a validated visual analogue scale of adherence [26]. Participants will also receive a one-time monetary compensation at the conclusion of the study (V3).

Table 1. Study Timeline and Data Collection

Study Visit	Subject identification	Baseline Visit (V1)	Visit 1A (V1A)	Visit 2 (V2)	Endpoint Visit (V3)
Time	-1 to -3 months	0	+1 month	+3 months	+6 months
Encounter Purpose	1-3 month Allopurinol washout	Study enrollment, Randomization, baseline values	UA titration, Adherence & Safety check	UA titration, Adherence & Safety check	Study endpoint
Data Collection of Treatment group	C, G	A-E, G	D, F	C, E, F	A-F
Data Collection of Control group	C	A-E	No visit	C	A-E
Data Collection key	A: Demographic, anthropometric, medication history, clinic BP B: Vital signs including 3 casual clinic BP measurements C: Standard of care lab work: Serum – Basic metabolic panel, UA, cystatin C; Urine – Protein, creatinine, UA D: Serum Comprehensive metabolic panel; urine UA, creatinine. E: Reserve residual serum and urine samples for biomarker analysis F: Pill count, Adherence visual analogue scale, Evaluation of adverse events G: Urine pregnancy test if applicable to females of reproductive age				

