2.2. Experimental Design: The study design of Aim 2 is the same as Aim 1 (see **Table 2**). We will measure the following biomarkers from reserved serum and urine samples at the baseline, 3, and 6 month visits. Activity of the Nlrp3 inflammasome will be measured via: serum high sensitivity CRP, Xanthine Oxidase

activity level, Nlrp3, Interleukins 1 β and 18, and urine Nlrp3 and IL-18. Renal injury biomarkers will be measured from serum NGAL, urine NGAL, NAG, KIM-1, and ET-1.

2.3. Statistical Analysis: We will report means/medians and standard deviations (SD)/interquartile range (IQR) for all continuous measures. Similar analyses will be used for Specific Aim 2 as Specific Aim 1. All sample size calculations were performed with nQuery Advisor v.7.0.

STUDY INTERVENTION ADMINISTRATION

The proposed intervention uses a study drug (Allopurinol) and concomitant therapy (Candesartan) that are available as generic. The PI is proposing to study the effects of Allopurinol under FDA-approved indications, which is approved for use in children and adults for the reduction of high uric acid levels. Candesartan is approved for use in children and adults for the reduction of high blood pressure. The concomitant therapy, Candesartan, is required in this protocol to reduce drug-drug interactions with Allopurinol. The medications Lisinopril, Enalapril, and Benazepril are commonly prescribed for hypertension but increase the risk of moderate to severe adverse reactions when used concomitantly with Allopurinol. Losartan is also a blood pressure lowering medication that uniquely lowers uric acid levels which could affect the results of the trial, but does not interact with Allopurinol so will be converted for a different and specific reason. Any participant in the trial who is prescribed Lisinopril, Enalapril, Benazepril, or Losartan at the time of randomization will be converted to a similar or same class of blood pressure lowering medication, Candesartan, which does not interact with Allopurinol or lower uric acid levels. Approximately 1/4 of participants in this trial will qualify for the Candesartan conversion. Candesartan will be supplied by the investigational pharmacy at no cost to participants. Allopurinol will also be supplied by the investigational pharmacy to the treatment group participants.

[figure not shown]
Recruitment and pre-trial medication adjustments:

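### Pregnancy excludes every participant, but Table 1 schedules the pregnancy test only in the Allopurinol row, so a scheduled test could detect an unrecognised pregnancy in one arm only

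*Combined protocol and SAP*

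**What the plan says.** The exclusion criteria in section 1.2 (Experimental Design) end with "Pregnant or nursing". Nothing limits this to one arm. Enrollment covers ages 2 to 20 and is not restricted by sex, so females of reproductive age can be in either group.

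Table 1 has one row headed "Data Collection of Treatment group" and one headed "Data Collection of Control group". Its key defines "G: Urine pregnancy test if applicable to females of reproductive age". G appears twice in the treatment row and never in the control row.

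On the timing of allocation, Table 1 puts randomization at the baseline visit (V1). The text on recruitment and pre-trial medication adjustments, under Study Intervention Administration, randomizes at consent those who need no washout or conversion, and the others after the washout. It then describes participants at the post-washout uric acid check as continuing in an arm already fixed. The same text allows consent by phone.

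Study-supplied Candesartan is not confined to the Allopurinol arm. It goes to any participant on one of four listed blood pressure drugs, and the plan expects that "Approximately 1/4 of participants in this trial will qualify for the Candesartan conversion".

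**The concern.** A criterion that defines the randomized population should be verified in the same way for everyone, before the arm is known. Removing participants found ineligible after randomization can be harmless if the finding rests on pre-randomization status and is sought equally in both arms. Here it is sought by a scheduled test in one arm only.

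The stake is comparability in an open-label trial. Section 1.3 and the Data and Safety Monitoring Plan both commit to intention-to-treat. The Specific Aims and the Background criticise the earlier pediatric Allopurinol trial for departing from that principle, so an arm-dependent check of eligibility would sit badly with the plan's own argument. There is also a practical gap: controls converted to Candesartan receive a study-supplied drug with no scheduled test behind the exclusion.

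**Working it through.** The plan gives no figure on this point, so the check is a comparison of Table 1 with the eligibility criteria and the timing text.

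**Step 1. Where the test is scheduled.** Codes as printed in Table 1:

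| Column | Treatment row | Control row | G in treatment / control |
|---|---|---|---|
| Subject identification (-1 to -3 months) | C, G | C | yes / no |
| V1 (0) | A-E, G | A-E | yes / no |
| V1A (+1 month) | D, F | no visit | no / no |
| V2 (+3 months) | C, E, F | C | no / no |
| V3 (+6 months) | A-F | A-E | no / no |

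Scheduled tests: 2 in the treatment row, 0 in the control row.

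**Step 2. Whether another item covers it.** The two laboratory items are "C: Standard of care lab work: Serum – Basic metabolic panel, UA, cystatin C; Urine – Protein, creatinine, UA" and "D: Serum Comprehensive metabolic panel; urine UA, creatinine". Neither includes a pregnancy test. A and B are history and vital signs, E is reserved sample, and F is adherence and adverse events. No other section schedules a test.

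**Step 3. Whether the arm is known when the test is done.**
- On Table 1's timing, the first G falls one to three months before randomization. No arm exists then, so a test assigned by arm cannot be carried out as written.
- The second G falls at V1, the visit at which Table 1 randomizes. The table does not say which comes first.
- On the recruitment text, participants who need no washout or conversion are randomized at consent, possibly by phone and so before a urine sample is in hand. G would then follow allocation.

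Differential removal is therefore possible under the third reading, possible under the second, and not possible under the first if everyone is tested.

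**Step 4. Scale.** Table 2 plans 28 Allopurinol and 14 control participants.
- One control is 1/14 = 7.1% of the control mean.
- If the plan's one quarter for Candesartan conversion applies equally to controls (an assumption), 14 × 1/4 = 3.5, or about 3 to 4 controls. Only some would be females to whom the test applies.
- Power is not the issue. The plan's inputs (difference 3, SD 3.5, one-sided alpha 0.05) give a noncentrality of 3 / (3.5 × √(1/28 + 1/14)) = 2.62 on 40 degrees of freedom and an exact t-test power of 0.824. This confirms the stated 80% or more. Losing one or two Allopurinol participants would leave 0.819 or 0.814.

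The number of pregnancies missed or removed cannot be calculated. The documents give neither a sex and age split nor a pregnancy rate.

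**The case against.** A reader might infer from Table 1 that the exclusion itself applies to one arm, that controls are excluded at a rate of zero by design, and that pregnant patients may enter as controls. The documents do not support this. The criterion is written once, for all participants, so a known or reported pregnancy, or nursing, excludes a control too. What is zero in the control row is the number of scheduled tests.

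A reader might also infer that the intention-to-treat comparison is already compromised. No section says that a participant who tests positive is removed after allocation. Since the first test precedes Table 1's randomization, the row placement may be no more than a notation slip, with the test meant for everyone. That stands as a possible reading, and it limits the point to a conditional one. It does not remove the inconsistency, because staff who follow the table as printed would test one arm.

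The test might instead be meant only as an Allopurinol safety check. That would explain the rows, but the exclusion would then need to be limited to that arm, and it is not.

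The Candesartan argument is secondary. Conversion is from one blood pressure drug to a similar one, and the documents do not tie the pregnancy exclusion to Candesartan.

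**Conclusion.** The point holds as an inconsistency between the exclusion criteria and the visit schedule. A trial-wide exclusion is backed by two scheduled tests in the Allopurinol row and none in the control row, so only an unrecognised pregnancy in the Allopurinol arm would be detected by a scheduled procedure.

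The threat to comparability is conditional. It arises if the test is done once allocation is known, and the conflicting statements on randomization timing leave that open. The number affected is probably small, sample size and power are not in question, and no bias in GFR change has been shown. The case for acting is that the contradiction is plain and cheap to remove, in an open-label trial with 14 controls that commits to intention-to-treat.

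**What to change.** Put item G in both rows of Table 1 as an eligibility check, completed before randomization for every female to whom it applies. Then reconcile the exclusion criteria, Table 1, the Candesartan conversion text and the recruitment text, so that they state one sequence: when eligibility is confirmed relative to randomization and to study-supplied medication changes.

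The test itself costs little. It adds a urine test for a few more participants, and item C already collects urine from both arms at subject identification and V1. The larger cost is procedural: those consented by phone, who under the current text could be randomized at consent, may have to wait until a urine sample is available. The sample size does not change.

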Aim 1. To determine the effect of Allopurinol treatment on GFR of hyperuricemic pediatric CKD patients. In a randomized controlled study, pediatric CKD patients with hyperuricemia (serum UA ≥ 5.5 mg/dL) will be allocated 2:1 to Allopurinol versus standard of care (SOC) control for 6 months. Participants will be stratified into two cohorts by disease etiology (cohort A: non-glomerular, cohort B: glomerular). Equal allocation of race is expected as our local population is composed of 50% black race. The primary outcome measure is the amount of GFR change from baseline to 6 months compared to the control group in both cohorts. Secondary outcomes are measurement of the amount of UA and BP change from baseline to 6 months.

Aim 2. Establish whether Allopurinol treatment reduces Nlrp3 inflammasome and renal injury biomarkers. In this exploratory aim, urine and serum biomarkers of Nlrp3 inflammasome activation (hs-CRP, XO enzyme activity, Nlrp3, IL-1 β , IL-18) and renal injury (KIM-1, ET-1, NAG, and NGAL) will be collected at 3 and 6 months and compared to baseline of cohorts A and B treatment and control groups.

Impact: GFR change from baseline to 6 months by treatment and cohort will be used to directly inform the effect size and sample size calculations required for a randomized controlled multicenter pediatric intervention trial. The simultaneous and novel exploration of the effect of XO inhibition on inflammation and renal injury biomarkers will provide crucial data that may identify mechanism of the XO inhibition effect.

BACKGROUND AND SIGNIFICANCE

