Pediatric CKD epidemiology is different from adult CKD in the following ways. First, the etiology is primarily due to non-glomerular diseases (e.g. congenital anomalies of the kidney and urinary tract [CAKUT], the most common cause at 50%), and glomerular diseases (e.g. acute glomerulonephritis) rather than the primary adult causes of diabetes and hypertension. CAKUT conditions and the resultant, often insidiously progressive, CKD is present from birth. Whereas the typical age of onset of glomerulonephritis is the teenage years with acute onset renal dysfunction leading often to a more rapid chronic progressive disease than non-glomerular CKD. In pediatrics, factors that affect the rate of renal function decline and lead to a faster progression of CKD towards end stage renal disease (ESRD) are black race, glomerular disease etiology, and modifiable disease phenotypes of hypertension, proteinuria, and hyperuricemia [2, 4].

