Results from adult clinical trials are often extrapolated to the pediatric population, but with the above listed differences in CKD epidemiology, the beneficial effect of UA lowering therapy should be tested separately in pediatrics. The effect of UA lowering therapy may differ for those with glomerular versus non-glomerular disease etiology, race, or for those with proteinuria versus none. There are data to support a similar beneficial effect from XO inhibitors in pediatrics as in adults, but the effect modification, if any, of these factors is not specifically known. For example, a single randomized placebo-controlled pediatric CKD trial of Allopurinol for 4 months demonstrated a statistically significant increase in the mean glomerular filtration rate (GFR) from baseline to endpoint of +16 ml/min/1.73m² (SD=9.3). However, this study did not report race, did not stratify participants by glomerular or non-glomerular disease etiology or presence of proteinuria, and did not use intention to treat principles when those with a pre-specified adherence rate <80% were excluded at the end of the study, leading to an overall study power of 78%. The reported rate of GFR change in adult trials range from approximately +1 to +3 ml/min/1.73m² (SD=1-3) [20]. While we recognize results in pediatric populations may differ from adults, further confirmation is needed before progressing to large scale trials. A feasibility pilot clinical trial proposed here will test the effect of XO inhibition on GFR using study design principles of blocked allocation of participants to control for known factors that affect GFR decline.

RESEARCH METHODS – Study Design

Specific Aim 1. To determine the effect of Allopurinol treatment on GFR of pediatric CKD patients with hyperuricemia.

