The allocation will be unblinded to investigators and participants. We plan to over-sample the glomerular cohort B and limit enrollment of the non-glomerular cohort A to ensure adequate distribution of the sample by disease etiology in a proportion generalizable to the national pediatric CKD population (2:1). The proposed allocation distribution is detailed in Section 1.3 and Table 2.

Hyperuricemia is defined in this protocol as having at least two measures of serum UA ≥ 5.5 mg/dL in the last 12 months, or actively treated with a XO inhibitor for a previous diagnosis of hyperuricemia. Participants actively treated with a UA lowering agent (Allopurinol, Febuxostat, or Losartan) will undergo a washout period of a minimum of 1 month (up to 3 months) prior to enrollment in the trial, then randomized to treatment versus control groups. None of the patients in the CHoR Pediatric Nephrology group practice actively treated with these agents had/have symptomatic hyperuricemia, and only 3 out of 14 treated have reached the target UA level of 3-5 mg/dL which will be applied in this study protocol. As it is unknown to what degree patients are benefiting from a minimal reduction of UA but with a persistent hyperuricemia, the CHoR Pediatric Nephrology Division has concluded that it is ethical for consenting participants actively receiving a XO inhibitor to be randomly assigned to treatment or control after a wash-out period.

Allopurinol dose will be initiated using standard weight-based dosing at the Baseline Visit 1 (V1), and titrated at Visits 1A and 2 (V1A, V2) to achieve a goal UA level in the normal range of 3-5 mg/dL by Visit 3 (V3).

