1.3. Statistical Analysis: We will report means/medians and standard deviations (SD)/interquartile range (IQR) for all continuous measures, and frequency and proportions for categorical variables. Assuming a clinically significant difference between treatment groups of 3 ml/min/1.73m² and individual group SDs=3.5, a one-sided analysis t-test performed at $\alpha=0.05$ will achieve at least 80% power for a sample size of 42 if the participants will be allocated in a 2:1 ratio between treatment and control. We will also enroll participants into two cohorts to assure proportional distribution between non-glomerular (cohort A) and glomerular (cohort B) disease etiology. Our local pediatric CKD population composition by disease etiology is similar to national proportions of approximately 70% non-glomerular and 30% glomerular disease etiology. We will therefore over-sample the glomerular sub-population in cohort B and limit enrollment of the non-glomerular cohort A to n=19, maintaining roughly a 2:1 proportion. The goal allocation enrollment by treatment group and cohort size is summarized in **Table 2**. Two-sample t-tests on the GFR change score will be used to address Specific Aim 1A while separate 2-way ANOVA models with an interaction will be used to address Aim 1B. Repeated measures ANOVA models will be used to inform from all three time points in an intent-to-treat fashion.

Table 2: Goal allocation enrollment

Treatment Group	Allopurinol Group	Control Standard of Care Group
Cohort A: Non-glomerular disease etiology	19	7
Cohort B: Glomerular disease etiology	9	7
Total	28	14

Specific Aim 2. Determine the effect of Allopurinol treatment on Nlrp3 inflammasome and renal injury biomarkers.

2.1. Rationale and Objective: To our knowledge there are no studies that explore the effect of XO inhibition on the known mechanism of hyperuricemia induced Nlrp3 inflammasome activation and renal injury in a clinical trial setting. We therefore propose to establish whether XO inhibition reduces levels of these biomarkers at 3 and 6 months compared to baseline. If our hypothesis is correct that inflammasome-mediated renal injury is improved by Allopurinol, we expect to find that after 3 and 6 months of Allopurinol treatment, the biomarker levels will be reduced from baseline in both treated cohort groups compared to control participants.

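### Table 2's cells contradict the 2:1 allocation within etiology cohorts and the cohort A limit of 19; enrolled as printed, they bias the unadjusted Aim 1A t-test toward Allopurinol if glomerular patients decline faster

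*Combined protocol and SAP*

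**What the plan says.** Aim 1 says hyperuricemic patients "will be allocated 2:1 to Allopurinol versus standard of care (SOC) control for 6 months". Section 1.1 proposes a "2:1 allocation between Allopurinol and standard of care (SOC) therapy, and stratified by disease etiology", with cohort A non-glomerular and cohort B glomerular. Section 1.2 sets the etiology mix at 2:1, non-glomerular to glomerular, and refers to Section 1.3 and Table 2 for the detailed allocation. Section 1.3 says the trial will over-sample cohort B and "limit enrollment of the non-glomerular cohort A to n=19, maintaining roughly a 2:1 proportion".

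Table 2 (Goal allocation enrollment) reads:

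| Cohort | Allopurinol | Control | Row total (my sum) |
|---|---|---|---|
| A, non-glomerular | 19 | 7 | 26 |
| B, glomerular | 9 | 7 | 16 |
| Total | 28 | 14 | 42 |

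For the analysis, Section 1.3 states: "Two-sample t-tests on the GFR change score will be used to address Specific Aim 1A". A two-way ANOVA with an interaction is reserved for Aim 1B, which Section 1.1 calls exploratory. A repeated measures ANOVA over the three time points is also planned, but its factors are not listed.

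**The concern.** The text and the table give different recruitment and randomization targets, and whoever builds the randomization list has to guess which one governs. The column sums in Table 2 are correct, so this is not a fault of text extraction.

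The second issue is confounding. The Background lists the factors behind "faster progression of CKD towards end stage renal disease (ESRD) are black race, glomerular disease etiology", and it ends by promising "blocked allocation of participants to control for known factors that affect GFR decline". Table 2 as printed does the opposite for etiology: it puts proportionally more of the faster-declining patients in the control arm. The primary t-test does not adjust for that. Part of any apparent drug effect could then be an etiology effect, in a pilot whose estimates are meant to set the effect size for a multicenter trial.

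**Working it through.** **Inputs from Section 1.3 and Table 2.** One-sided α = 0.05; difference 3 ml/min/1.73m²; SD 3.5 in each group; N = 42 at 2:1; cells 19:7 and 9:7.

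**Input not in the documents.** d is the mean 6-month GFR change in non-glomerular patients minus that in glomerular patients. The Background gives its direction (glomerular disease progresses faster), and Section 1.1 says the size is uncertain. I assume d = 0 to 5.

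**1. The plan's own power.** For 28 against 14, SE = 3.5 × √(1/28 + 1/14) = 1.146, so the noncentrality is 3/1.146 = 2.62 on 40 df. Power is 82.4%. The stated figure of at least 80% reproduces. It depends only on the arm totals, so the cells do not affect it.

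**2. Ratios in Table 2.**
- Cohort A: 19/7 = 2.71.
- Cohort B: 9/7 = 1.29.
- Arms: 28/14 = 2.00.
- Etiology mix: 26/16 = 1.63, against 28:14 for an exact 2:1.
- Cohort A total: 19 + 7 = 26, against a limit of 19. A true limit of 19 would leave 42 − 19 = 23 in cohort B, which reverses the intended mix.

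**3. What 2:1 in both directions would give.** Cohort A: 28 × 2/3 = 18.7 and 28/3 = 9.3. Cohort B: 14 × 2/3 = 9.3 and 14/3 = 4.7. The nearest whole numbers are 19:9 and 9:5. The printed Allopurinol column (19, 9) fits; the control column (7, 7) does not.

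**4. Bias if the printed cells are enrolled.** The glomerular share is 9/28 = 0.321 on Allopurinol and 7/14 = 0.500 on control. With no drug effect, the expected unadjusted difference is d × (0.500 − 0.321) = 0.179d, in favor of Allopurinol.

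**5. Type I error.** Simulated with the printed cells, no drug effect, within-cohort SD 3.5, one-sided nominal 5%, 400,000 replicates per value of d:

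| Assumed d | Bias | Unadjusted t-test | With etiology term |
|---|---|---|---|
| 0 | 0 | 5.0% | 5.0–5.1% |
| 1 | 0.18 | 6.6% | 5.0–5.1% |
| 2 | 0.36 | 8.1% | 5.0–5.1% |
| 3 | 0.54 | 9.3% | 5.0–5.1% |
| 5 | 0.89 | 10.9% | 5.0–5.1% |

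Reading 3.5 as the total SD instead gives 6.6%, 8.1%, 9.6% and 11.0% at d = 1, 2, 3 and 5.

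**6. Power with etiology in the model.** SE = 3.5/√(Σ n₁n₂/(n₁ + n₂)), summed over the two cohorts, with 39 df.
- Printed cells: 19×7/26 + 9×7/16 = 9.05, SE 1.163, power 81.3%.
- 19:9 and 9:5: 19×9/28 + 9×5/14 = 9.32, SE 1.146, power 82.3%.
- 18:9 and 10:5: 18×9/27 + 10×5/15 = 9.33, SE 1.146, power 82.3%.

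**7. Unadjusted bias with corrected cells.** For 19:9 and 9:5 the shares are 9/28 = 0.321 and 5/14 = 0.357, so the bias is 0.036d (0.04 to 0.18 for d = 1 to 5). For 18:9 and 10:5 it is zero. The unadjusted test then becomes conservative at larger d, because it leaves the etiology variance in the error term: type I error is 3.7% at d = 3 and 2.3% at d = 5 with 18:9 and 10:5 (200,000 replicates).

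**The case against.** The bias depends on two conditions: the printed cells must actually be enrolled, and d must be sizeable. The text describes stratified 2:1 randomization, which would largely remove the imbalance, and Table 2 is labeled as a goal. At d = 1 the bias is only 0.18, and d = 5 exceeds both the design difference and the SD. This stands, and the size is therefore given only as a conditional range. But Section 1.2 names Table 2 as the detailed allocation, so the first condition cannot be ruled out.

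The etiology-mix conflict is mild. Section 1.3 asks only for an approximate 2:1 and intends to over-sample glomerular patients, and 16/42 = 38% does so. That is fair, and this is the weakest of the discrepancies. The limit of 19 may be a slip in which one cell was taken for the cohort total. That is plausible, but the documents do not settle it.

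The Aim 1A test could also be read as one t-test per cohort, since Aim 1 mentions both cohorts. Those estimates would not be distorted. Section 1.1, however, defines the Aim 1A outcome by treatment group, which points to a pooled test. The repeated measures model has no stated etiology term, so it cannot be counted as protection.

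Finally, the corrected cells weaken the glomerular comparison. For a 3-unit effect, cohort B power falls from about 49% (9:7) to 42% (9:5) or 44% (10:5), while cohort A power rises from 59% to 66% or 65%. This is a real trade-off for exploratory Aim 1B, but the plan states no power for that aim.

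**Conclusion.** The concern holds. The text and Table 2 disagree on allocation within cohorts and on the size of cohort A, and less sharply on the etiology mix. These contradictions rest on no assumption.

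The bias is conditional. If the printed cells are enrolled and Aim 1A is a pooled, unadjusted t-test, the comparison is shifted by 0.179d toward Allopurinol. At d = 3 that is 0.54 ml/min/1.73m², or 18% of the 3-unit design difference, with a one-sided type I error near 9%. The direction comes from the Background; the size of d is assumed. The sample size, the arm totals and the stated power stand. This should be fixed before the randomization list is built.

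**What to change.** 1. Reconcile Table 2 with the stated allocation, keeping N = 42 and 28:14 by arm. One option is 19:9 in cohort A and 9:5 in cohort B, which changes only the two control cells and gives a 28:14 etiology mix. Another is 18:9 and 10:5 (27:15), which is exactly 2:1 within each cohort. If the 7:7 control split is deliberate, say so, give the reason, and amend the 2:1-within-strata wording.
2. State the cohort A limit as the cohort total that matches the chosen table (28 or 27 in these examples), not 19.
3. Make the primary Aim 1A analysis a linear model of GFR change on treatment and etiology cohort. This removes the etiology bias whichever cells are enrolled, and it avoids the conservatism of an unadjusted test after stratified randomization.

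The cost is a table edit, one sentence and one model term. No extra patients are needed. The term uses one degree of freedom, and power is 81.3% with the printed cells or 82.3% with corrected ones, against 82.4% unadjusted. The authors should weigh the lower cohort B power when choosing the cells.

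### The Aim 1A primary test is an unadjusted t-test on GFR change that omits the etiology stratum, which the plan itself treats as prognostic, and baseline GFR

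*Combined protocol and SAP*

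**What the plan says.** Section 1.1 defines the endpoint: "The primary outcome of Aim 1A is change in GFR between baseline and 6 months by treatment group". Section 1.3 gives the test: "Two-sample t-tests on the GFR change score will be used to address Specific Aim 1A". It names no stratum or covariate.

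The design does use etiology. Under Aim 1, "Participants will be stratified into two cohorts by disease etiology (cohort A: non-glomerular, cohort B: glomerular". The Background describes glomerulonephritis as "leading often to a more rapid chronic progressive disease than non-glomerular CKD" and lists glomerular etiology among the factors behind faster progression. The Specific Aims and Background also fault the earlier pediatric trial for not stratifying on known modifiers.

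In the analysis, etiology appears only at a lower level. Section 1.1 says "An exploratory sub-aim (Aim 1B) will identify and compare GFR change by cohort characteristics", and section 1.3 assigns two-way ANOVA models with interaction to that sub-aim. Section 1.3 also mentions repeated-measures ANOVA over the three time points, but names no covariates for it and does not call it primary.

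**The concern.** A factor important enough to stratify on, and described as affecting the rate of decline, would normally be in the model that decides the primary question. Leaving it out has two possible consequences.

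- **Balanced cells.** The t-test's variance estimate includes the between-cohort spread, which stratification has already removed from the treatment contrast. The test is then conservative and loses some power.
- **Unbalanced cells.** If the etiology mix differs by arm, the unadjusted difference carries part of the etiology effect, and the error rate moves away from 5%.

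Baseline GFR is a related but weaker point. A change score subtracts the baseline but does not adjust for any relation between baseline and change, and participants with CKD stages 1 to 5 are eligible.

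The estimate matters beyond this pilot, because the Impact paragraph says it will set the effect size and sample size of a multicenter trial.

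**Working it through.** **1. The plan's own figure.** Section 1.3 supplies the inputs: "Assuming a clinically significant difference between treatment groups of 3 ml/min/1.73m²", "individual group SDs=3.5", one-sided alpha 0.05, and 42 participants at 2:1 (28 and 14).

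- Standard error = 3.5 × √(1/28 + 1/14) = 3.5 × 0.3273 = 1.146.
- Noncentrality = 3 / 1.146 = 2.62, with 40 degrees of freedom.
- Exact noncentral-t power = 82.4%. The smallest total at exact 2:1 that reaches 80% is 42, so the stated figure reproduces.

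**2. Assumptions for the comparison.** D is the non-glomerular minus glomerular difference in six-month GFR change. The documents do not give it, so values of 0, 1, 2 and 3 are used, with glomerular disease declining faster. The SD of 3.5 is taken as the spread within a treatment group with cohorts mixed. Each setting has 200,000 simulated trials of 42 participants. The simulation error on a power near 82% is √(0.82 × 0.18 / 200,000) = 0.0009, or about 0.1 point, so gaps of 0.2 point between runs are noise.

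**3. Both cohorts filled 2:1 (18:9 and 10:5).** The cohort A share is 27/42 = 0.643 in each arm, so there is no shift. Within-cohort SD = √(3.5² − D² × 0.643 × 0.357).

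| D | Within-cohort SD | Type I error, t-test | Power, t-test | Power, with cohort |
|---|---|---|---|---|
| 0 | 3.50 | 5.0% | 82.3% | 82.2% |
| 1 | 3.47 | 4.8% | 82.7% | 83.1% |
| 2 | 3.37 | 4.4% | 83.3% | 85.0% |
| 3 | 3.19 | 3.5% | 84.4% | 88.1% |

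With cohort in the model, type I error is 5.0% to 5.1% throughout. The power gain is nil at D = 0, then 0.4, 1.7 and 3.7 points.

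**4. Table 2 filled as printed (19:7 and 9:7).** The glomerular share is 9/28 = 32% on allopurinol and 7/14 = 50% on control. Shift = D × (0.500 − 0.321) = 0.179 × D, toward allopurinol.

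| D | Shift | Type I error, t-test | Type I error, with cohort |
|---|---|---|---|
| 0 | 0 | 5.1% | about 5% |
| 1 | 0.18 | 6.6% | about 5% |
| 2 | 0.36 | 8.2% | about 5% |
| 3 | 0.54 | 9.6% | about 5% |

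Reading 3.5 as the SD within cohort changes little. For D = 1, 2 and 3 the t-test's type I error is 4.9%, 4.4% and 3.8% with 2:1 cells, and 6.6%, 8.2% and 9.4% with Table 2 cells.

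**5. Adding baseline GFR (D = 0, 2:1 cells).** The correlation of baseline GFR with change is assumed. Cohort alone gives 82.4%.

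| Correlation | Power, cohort and baseline |
|---|---|
| 0 | 81.6% |
| 0.1 | 81.7% |
| 0.2 | 82.6% |
| 0.3 | 84.5% |
| 0.5 | 90.0% |

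Adjustment breaks even at a correlation of about 0.2. Below that the loss is under one point.

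**6. Cost if neither covariate is prognostic.** Power falls from 82.3% to 81.4% with 2:1 cells, and from 82.4% to 80.3% with Table 2 cells.

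**The case against.** Under 2:1 allocation within strata, the planned test is valid. Its type I error never exceeds 5% and its power stays above 80%, so no stated property of the plan fails. That is correct, and it limits the point to an improvement.

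The gain of nearly 4 points needs D = 3, an etiology gap as large as the whole assumed treatment effect. At D = 1 the gain is 0.4 point. The Background gives a direction for D but no size. This also stands.

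Error-rate inflation arises only if Table 2 is filled as printed. Those cells do not fit 2:1 within each cohort, and 19 + 7 = 26 conflicts with the section 1.3 limit of 19 for cohort A. Correcting the table would remove the shift with the t-test unchanged, so the inflation is conditional. Even so, sections 1.2 and 1.3 present Table 2 as the enrollment target, and a model with cohort keeps its error rate however the cells fill.

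No passage calls baseline GFR prognostic. That half rests on an assumed correlation and the wide range of eligible CKD stages, and it is the weaker half. With no stated dropout allowance, 80.3% in the least favorable case also leaves little margin.

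The Aim 1B and repeated-measures models touch on etiology and baseline, but neither is the test named for Aim 1A.

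Finally, Aim 1 speaks of both cohorts and section 1.3 uses the plural for the t-tests, so separate tests by cohort are a possible reading. The sample size, however, is for one pooled comparison. Separate tests on the Table 2 cells would have only 59% power (19 against 7) and 49% power (9 against 7).

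**Conclusion.** The point holds, as a change worth considering. The test that decides Aim 1A ignores the factor on which the trial is stratified, and uses baseline GFR only by subtraction. The planned power is not breached.

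With 2:1 cells the loss is 0 to about 4 points of power for D from 0 to 3. With Table 2 cells the same test would run at 6.6% to 9.6% one-sided for D from 1 to 3, against about 5% once cohort is in the model.

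These sizes rest on an assumed D, on the plan's SD of 3.5 and effect of 3, on the pooled reading of the test, and on 42 complete participants. The case for cohort is firmer than the case for baseline GFR, which pays only if its correlation with change is about 0.2 or more.

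**What to change.** Prespecify the Aim 1A primary analysis as an ANCOVA of six-month GFR, or of change, on treatment group, etiology cohort (A or B) and baseline GFR. With baseline in the model, either outcome gives the same treatment estimate. Report the adjusted difference with its confidence interval and keep the unadjusted t-test as a sensitivity analysis. Use the same form for uric acid and blood pressure, each with its own baseline. The Aim 1B interaction models can stay as they are. As a separate correction, reconcile Table 2 and the cohort A limit with 2:1 allocation.

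Only SAP wording changes. Etiology is recorded at baseline, and section 1.2 already provides the GFR samples: "Serum and non-invasively obtained urine will be collected at baseline, 3, and 6 months". The price is two degrees of freedom, with the power loss shown in step 6 of the working if neither covariate is prognostic.
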